5.1 Participant Inclusion Criteria

- 1. Males and females at least 18 years of age.
- 2. Voluntary written informed consent before performance of any study-related procedure.
- 3. Subject must have documented relapsed or refractory multiple myeloma in need of therapy, after at least one previous line of therapy for myeloma.
- 4. Eastern Cooperative Oncology Group (ECOG) performance status score of ≤ 2 .
- 5. Willingness and ability to participate in study procedures.

5.2 Participant Exclusion Criteria

- 1. Anti-myeloma treatment within 2 weeks prior to Cycle 1, Day 1.
- Cumulative dose of corticosteroids greater than or equal to the equivalent of 140mg prednisone for ≥4 days or a dose of corticosteroids greater than or equal to the equivalent of 40 mg/day of dexamethasone for ≥4 days within the 2-week period prior to Cycle 1, Day 1.
- 3. Previous allogeneic stem cell transplant; or Autologous Stem Cell Transplantation (ASCT) within 12 weeks before Cycle 1, Day 1.
- 4. Clinical signs of meningeal involvement of multiple myeloma.
- 5. Clinically significant cardiac disease, including:
 - a) Myocardial infarction within 6 months, or unstable or uncontrolled condition (e.g., unstable angina, congestive heart failure, New York Heart Association Class III-IV).
 - b) Cardiac arrhythmia (CTCAE Grade 2 or higher) or clinically significant ECG abnormalities.

- c) ECG showing a baseline QT interval as corrected by Fridericia's formula (QTcF) >470 msec.
- 6. Known active hepatitis B, or C.
- 7. Known HIV infection.
- 8. Prior or concurrent malignancy, except for the following:
 - a) Adequately treated basal cell or squamous cell skin cancer.
 - b) Any cancer (other than in-situ) from which the subject has been disease-free for 3 years prior to study entry.
- 9. Any of the following laboratory test results during Screening:
 - a) Absolute neutrophil count $\leq 1.0 \times 10^{9}$ /L;
 - b) Hemoglobin level \leq 7.5 g/dL (\leq 5 mmol/L);
 - c) Platelet count <75 × 10⁹/L in patients in whom <50% of bone marrow nucleated cells are plasma cells and <50x10⁹/L in patients in whom more than 50% of bone marrow nucleated cells are plasma cells;
 - d) Alanine aminotransferase level \geq 2.5 times the upper limit of normal (ULN);

10. Pregnant or nursing women.

5.3 Duration of the study

Patients will receive therapy until disease progression or as per physician's decision regarding the patient's best interest and according to the approved indications. Study accrual and collection of data will be completed in two years. The study can be terminated for any reason and at any time by the Sponsor.

5.4 Participant Withdrawal or termination

5.4.1 Reasons for Withdrawal or Termination

Every patient has the right to discontinue study participation at any time, for any reason, and every patient may be discontinued from the study for any reason beneficial to his/her well-being.

Subjects MUST discontinue for any of the following reasons:

- Withdrawal of informed consent.
- Any adverse event (AE), laboratory abnormality or intercurrent illness that, in the opinion of the investigator, indicates that continued participation in the study is not in the best interest of the subject.
- Pregnancy.
- Progressive Disease.

5.4.2 Handling of Participant Withdrawals or Termination

All patients, except those who withdraw consent, will be followed up according to the study procedures.

5.5 Premature Termination or Suspension of Study

The study can be terminated for any reason and at any time by the Sponsor.

6. Study research strategy - Technical description

6.1 Population and treatment

6.1.1 Population

The study will include patients with relapsed or refractory multiple myeloma who have received at least one prior line of therapy (2) and who according to physicians decision are treated with carfilzomib dexamethasone in the approved indication, doses and schedule. Briefly, patients aged 18 years or older with relapsed or refractory multiple myeloma, Eastern Cooperative Oncology Group performance status of 0 to 2, at last one prior treatments, will be included (see section 5.1 & 5.2).

6.1.2 Carfilzomib treatment

According to the approved indications patients will be given carfilzomib at a dose of 20 mg/m² on days 1 and 2 of cycle 1; and thereafter at a dose of 56 mg/m², in a 30 min intravenous infusion, on days 1,2,8,9,15 and 16. Dexamethasone (40mg IV) will be administered 24-48 hours before first CFZ infusion in order to assess the individual vascular effects of each drug separately; subsequently dexamethasone will be given IV at a dose of 20 mg on days 1,2,8,9,15 and 16, and orally on days 22 and 23 of a 28-day cycle. The rationale for using these doses is based on the results of the ENDEAVOR study and the approved indications and dosing of KYPROLIS. Intravenous hydration (250-500 mL before and after dose administration) is going to be given during cycle 1 and at the investigator's discretion thereafter.

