2. Potential risks and benefits

This is an observational, non interventional, prospective study. Patients with relapsed or refractory multiple myeloma who have received at least one prior line of therapy and who receive carfilzomib with dexamethasone according to the approved dose and schedule (2) will be included in this observational study. No specific treatment intervention related to the study is going to be performed. No specific harms or benefits are expected due to study investigations.

3. Objectives and Purpose

The present study will assess patients with multiple myeloma receiving the proteasome inhibitor carfilzomib (CFZ), in order to investigate, *in vivo*, a wide spectrum of human atherosclerosis indices, from cardiovascular risk factors to subclinical atherosclerosis at multiple successive stages in a human model under conditions of global UPS inhibition, and correlate with cardiovascular complications associated with carfilzomib therapy, in patients receiving carfilzomib with dexamethasone.

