6.2.4 Ankle Brachial Index (ABI)

The ABI is a simple, non-invasive diagnostic test for lower-extremity peripheral arterial disease (PAD) with high validity of the test for stenosis \geq 50% in leg arteries (sensitivity \approx 95% and specificity \approx 100%) (33). The ABI can be easily measured by the means of ordinary blood pressure cuff and a Doppler ultrasonic sensor. The blood pressure cuff is used to measure systolic blood pressure in the brachial artery of both arms by use of the Doppler detector in the antecubital fossa. The blood pressure cuff is then applied to the ankle, and the Doppler probe is used to determine systolic blood pressure at the left and right posterior tibial arteries and dorsalis pedis arteries. The ABI for each leg equals the ratio of the higher of the 2 systolic pressures (posterior tibial or dorsalis pedis) in the leg and the average of the right and left brachial artery pressures, unless there is a discrepancy \geq 10 mm Hg in blood pressure values between the 2 arms. An ABI <0.90 in either leg is considered evidence of PAD, and progressively lower ABI values indicate more severe obstruction. Besides an indicative marker for leg artery disease ABI has been shown to serve as a surrogate marker for atherosclerosis having at the same time predictive value future cardiovascular events, independent of established risk factors(34).

All the above mentioned vascular measurements will be performed at each time point, that is on baseline and days 1,2,8,9,15 and 16 of cycle 1 and on days 1,2 of cycle 2 and 3 before and 2 hours after drug administration. The B-Mode ultrasound of the carotid and femoral arteries will only be performed at baseline. On cycle 6 all vascular measurements will be repeated to assess the chronic effect of proteasome inhibition on vascular function and atherosclerosis. Subjects will be instructed to fast overnight, to refrain from smoking, ingesting alcohol or caffeine on the day of testing and to hold any vasoactive medications for 12 h before the imaging studies.

6.2.5 24-hour Ambulatory Blood Pressure Monitoring (ABPM)

Patients will have their blood pressure monitored for 24 hours during the 1st day of cycles 1, 2, 3 and 6.

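### Only dexamethasone is measured alone: every carfilzomib measurement day also carries dexamethasone, so the stated separate assessment of each drug is not delivered, and the lead-in's measurement purpose needs reconciling with the non-interventional statement

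*Protocol*

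**What the plan says.** Section 6.1.2 sets out the treatment. The lead-in reads "Dexamethasone (40mg IV) will be administered 24-48 hours before first CFZ infusion", and its stated reason is "in order to assess the individual vascular effects of each drug separately". After that, "subsequently dexamethasone will be given IV at a dose of 20 mg on days 1,2,8,9,15 and 16". Carfilzomib is given "in a 30 min intravenous infusion, on days 1,2,8,9,15 and 16", at 20 mg/m² on days 1 and 2 of cycle 1 and 56 mg/m² thereafter. Hydration, 250-500 mL before and after the dose, "is going to be given during cycle 1 and at the investigator's discretion thereafter".

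The section 7 schedule has measurements before and after dexamethasone at d-2. The legible headings of the later columns refer to the combination, abbreviated CarD. The synopsis also lists measurements around dexamethasone and around carfilzomib, with 2-hour and 24-hour times.

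The protocol describes its target in two ways. The Background (section 1) and section 4.1 A speak of the effect of a proteasome inhibitor and of the acute response to carfilzomib. The sample size hypothesis in section 6.1.3 concerns CFZ/Dex therapy.

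On status, section 2 states: "No specific treatment intervention related to the study is going to be performed". Sections 6.1.1 and 6.1.3 and the synopsis likewise describe a non-interventional study or treatment as approved. Section 6.2.4 tells patients to "hold any vasoactive medications for 12 h before the imaging studies".

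**The concern.** The lead-in is presented as the device that separates the two drugs. It would do so only if each drug, or a known combination with the other held equal, were observed somewhere. Here one drug is observed alone and the other only in company, and the dexamethasone that accompanies it is at a different dose from the lead-in.

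The endpoints at stake are blood pressure, endothelial function, arterial stiffness and wave reflections, the primary endpoints of the study. Dexamethasone and volume loading are present on the same days as the acute cycle 1 measurements. If the report followed the wording of section 4.1 A, an acute change on day 1 would be credited to carfilzomib or to proteasome inhibition, with no design feature that excludes the other two exposures.

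The second matter is consistency. A drug administration whose stated reason is a study measurement sits beside a statement that the study performs no treatment intervention of its own.

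**Working it through.** The protocol gives no figure on this point to reproduce. The check is a count of exposures and then an argument about what can be estimated.

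**1. Exposures on carfilzomib measurement days**

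- Schedule in section 7, reading d0 as the first infusion day: d0, d2, d8, d9, d15, d16, C2d1, C2d2, C3d1, C3d2, C6d1 = 11 days. The last may instead fall 6 months after baseline.
- Synopsis: the same 10 days through cycle 3, plus days 1, 2, 15 and 16 of cycle 6 = 14 days.
- Dexamethasone is fixed on the same days as carfilzomib: 11 of 11, or 14 of 14. Carfilzomib without dexamethasone: 0 of 11, or 0 of 14.
- Hydration is fixed in cycle 1 only: 6 of 11, or 6 of 14. It is discretionary on the other 5, or 8.

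**2. What each change measures**

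Assume additive effects on the post-minus-pre change: D40 and D20 for dexamethasone 40 mg and 20 mg, C for carfilzomib, F for fluid.

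| Occasion | Change contains |
|---|---|
| d-2 | D40 |
| Cycle 1 | C + D20 + F |
| Later cycles, if no fluid is given | C + D20 |

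C and D20 enter every carfilzomib occasion together, each with weight 1. Any weighted combination of occasions that gives C a total weight of 1 therefore also gives D20 a weight of 1, so C cannot be isolated. A rank check agrees. With d-2 and cycle 1 the rank is 2, rising to 3 when C is added as a target. With fluid-free later cycles included it is 3, rising to 4. A target that raises the rank is not estimable.

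**3. The d-2-subtracted contrast**

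(C + D20 + F) - D40 = C + (D20 - D40) + F.

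This equals C only if the two dexamethasone doses have the same effect and fluid has none. The protocol also does not say whether the pre-dose measurement falls before or after the pre-dose fluid, so how much of F enters is unknown.

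**4. Assumptions that would rescue it**

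If D20 is taken as a known multiple of D40, C is still not estimable from d-2 and cycle 1 with C treated as one constant. It becomes estimable only when some later measurements are fluid-free and there is no carry-over, no time trend and the same C in all cycles. The protocol states none of these.

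**5. The day 8 versus day 1 contrast**

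Write C20 and C56 for the two carfilzomib doses. Dexamethasone and hydration are nominally unchanged within cycle 1:

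(C56 + D20 + F) - (C20 + D20 + F) = C56 - C20.

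This removes dexamethasone and fluid, but it is a dose contrast and not the effect of either dose. It is confounded with time and prior exposure. Turning it into an effect needs a dose-response assumption: under strict proportionality C56 = (56/20) x C20 = 2.8 x C20, and the contrast is 1.8 x C20. The protocol makes no such assumption.

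**6. Mixed models**

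The linear mixed models in section 8 do not supply the missing information, because dexamethasone does not vary independently of carfilzomib from day 1 onward.

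**7. Status statements side by side**

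Section 2 denies a study-related treatment intervention. Section 6.1.2 gives the lead-in a measurement purpose, and also says that the doses rest on a cited randomised phase 3 trial and on approved dosing. The second statement explains the doses; it does not remove the purpose given for the lead-in.

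**The case against.** The primary objective and the hypothesis in section 6.1.3 concern carfilzomib with dexamethasone, so the quantity that the study was sized for does not depend on isolating carfilzomib. That stands, and it limits the finding to the attribution claim.

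There is also more within-patient information than the d-2 comparison: the rise in carfilzomib dose by day 8, and the planned comparison of vascular change with the degree of change in proteasome activity (section 4.1). Both stand as evidence bearing on attribution. Neither yields a carfilzomib-alone effect without further assumptions.

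Detailed contrasts can be left to a statistical analysis plan. That also stands; the finding rests on the property claimed in section 6.1.2, not on an absent contrast.

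On status, the 12-hour drug hold appears beside fasting, smoking and caffeine instructions and may be seen as ordinary preparation for measurement. It needs clarifying and is not a plain contradiction. The lead-in is different, because the protocol itself states a measurement purpose for it.

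**Conclusion.** The point holds for attribution and for consistency. Section 6.1.2 claims a property that the design has for dexamethasone and lacks for carfilzomib: 0 of 11 carfilzomib measurement days (0 of 14 by the synopsis) are without dexamethasone. The algebra assumes additive effects; the count needs no such assumption. Separately, the measurement purpose of the lead-in conflicts on its face with section 2.

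Several stronger conclusions might be inferred, and the documents do not support them:

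- *That fluid accompanies every carfilzomib measurement.* It is fixed in cycle 1 only.
- *That day 1 against d-2 is the only within-patient comparison.* Day 8 against day 1 is another.
- *That a loss of detectable difference can be quoted.* The protocol states neither an SD for the change nor a correlation between the two changes. With equal SDs the contrast has variance 2 x SD² x (1 - r), which exceeds that of a single change when r is below 0.5 and falls below it when r is above 0.5.
- *That the lead-in departs from approved dosing, or that the study is in truth interventional.* The approved schedule is not among the documents. They show only that the statements must be reconciled.

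The finding should be acted on, but it does not invalidate the combined-treatment analysis.

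**What to change.** - In section 6.1.2, replace the claim of separate assessment. State that d-2 estimates dexamethasone alone and that day 1 onward estimates carfilzomib plus dexamethasone, with hydration in cycle 1 and possibly later.
- Align the wording in section 1 and section 4.1 A on the effect of, or response to, carfilzomib with the CFZ/Dex hypothesis in section 6.1.3.
- Report two contrasts as supportive only: (day 1 post minus pre) minus (d-2 post minus pre), limited by the dexamethasone dose difference and fluid; and the day 8 change against the day 1 change, as a carfilzomib dose contrast confounded by time and prior exposure. State these limits and make no carfilzomib-alone claim.
- Reconcile sections 2, 6.1.1, 6.1.2 and 6.1.3 on whether the lead-in is a study-related intervention, and clarify in the same way the vasoactive drug hold in section 6.2.4. No dose, schedule or clinical rule is proposed here; the sponsor must settle which statement is meant.

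The cost is wording and two contrasts from measurements already scheduled. The downside is a weaker attribution claim.

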6.1.3 Sample size

This is an observational study with non interventional design. Sample size calculation is made on the basis of previous data indicating that at least 2% absolute difference in Flow mediated dilatation (FMD) (corresponding to 20-30% relative difference) is considered significant and clinically relevant. With the null hypothesis being that CFZ/Dex therapy is associated with <10% relative difference in FMD and the alternative hypothesis being that a \geq 30% difference is considered as significant, and with an a=0.05, a sample of 40 patients is required for 90% power of detecting these differences (all tests are 2-sided). A dropout rate of 15% is assumed. A total number of 46 patients is thus calculated to be enrolled.

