Objectives:	 Primary to describe cardiovascular complications associated with the use of carfilzomib and investigate the role of the UPS inhibition, in patients treated with carfilzomib and dexametahsone, on atheromatosis and vascular inflammation and function 						
	 Secondary to outline the clinical significance of carfilzomib toxicity in hemodynamic parameters and cardiovascular function and vascular structure 						
Endpoints	 Primary Changes in hemodynamic markers (peripheral and aortic office blood pressure and 24 hour ambulatory BP monitoring parameters) and in peripheral vascular function (endothelial function, arterial stiffness, arterial wave reflections) before, during and after study drug administration 						
	 Secondary Changes in subclinical atherosclerosis markers (carotid intima-media thickness and vascular wall and plaque echogenicity) changes in markers of cardiac function (ejection fraction, 						

Population:	 systolic and diastolic strain and strain rate) changes in circulating cardiac and vascular inflammatory biomarkers (NtproBNP, cTnT, C-reactive protein, interleukin 6, vascular cell and intercellular adhesion molecule-1, E-selectin, and monocyte chemoattractant protein-1) before and after study drug administration Patients with relapsed or refractory myeloma treated with carfilzomib as per approved indications
Phase:	This is an observational, non interventional, prospective study
Number of Sites:	This is a single center study
Description of Study assessments:	Patients with an indication to receive carfilzomib & dexamethasone will be treated according to approved dose and schedule
	A. Vascular studies: Vascular measurements will be performed at baseline before and after dexamethasone, before and after CFZ administration, 2 hours and 24 hours after CFZ administration. These measurements will be repeated on days 8,9,15 and 16 of cycle 1, on days 1,2 of cycles 2 and 3 and days 1,2,15 and 16 of cycle 6 or earlier if the patient develops progression of disease. Vascular measurements include assessment of arterial stiffness, arterial wave reflections, subclinical carotid and femoral atherosclerosis and carotid plaque composition, using non-invasive well-validated techniques. Blood pressure will be evaluated using 24h hour ambulatory monitoring at baseline and on days 1 and 8 of cycle 1 and at the beginning of cycles 2, 3 and 6.

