6.5 Measurement of circulating cardiac and vascular inflammatory biomarkers

Plasma and serum samples will be obtained by venipuncture on admission and stored at - 70°C. Plasma probes will be centrifuged for 15 minutes at 10.000 g within 30 minutes of

collection. Probes will be aliquoted and stored at -70°C till analysis. The concentrations of Creactive protein, interleukin 6, vascular cell and intercellular adhesion molecule-1, E-selectin, and monocyte chemoattractant protein-1 will be measured in ethylenediaminetetraacetic acid (EDTA)-plasma at the Oncology Laboratory of the Department of Clinical Therapeutics wellcharacterized enzyme immunoassays. N-terminal pro-B-type natriuretic peptide will be measured with a sandwich immunoassay on an Elecsys 2010 instrument (Roche Diagnostics). Serum cardiac troponin T concentrations will be measured using statndard procedures.

7. Timelines of the study

Vascular measurements and blood collection will be performed at baseline before and 2 hours after dexamethasone and carfilzomib administration. These measurements will be repeated as shown below:

	Before Dexa	After Dexa	Before & after CarD	After CarD	Before & after CarD								
Time points	d -2		d0	d2	d8	d9	d15	d16	C2d1	d2	C3d1	d2	C6d1or 6 months after baseline
Vascular studies	x	X	X†	X	Xt	X	Xt	X	Xt	X	Xt	x	t x
24h ambuatory BF monitoring	×		X*		Х*				X*		X*		X*
Cardiac US	X					1				. 8			X**
Blood for Proteasome activity			x	x	x	x	X?	x	x	x			Xt
Serum collection for cardiac biomarkers	×		×t		×t		×t		×t		x		x

Schedule of assessments

* During 24th of CarD

**Only before C6d1

†2 measurements/ samples at this day

The subjects will be evaluated for AE at all visits.

8. Data presentation and statistical analysis

Data will be presented as mean ± standard deviation (SD). Continuous variables will be tested for normal distribution with the Kolmogorov-Smirnov test. Repeated measures ANOVA will be performed in order to assess significant variations of parameters of interest over time. Linear mixed models analysis will be performed in order to adjust for possible confounders over time. All tests will be two-tailed and statistical significance will be considered for P

values less than 0.05. All statistical analyses will be performed using SPSS version 21 for windows (Chicago, ILL, USA).

9. Safety reporting

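### The sample size is justified against a null of less than 10% relative change in FMD, but the planned repeated measures ANOVA tests a null of no change, so the stated 90% is not the power of the planned test

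*Protocol*

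**What the plan says.** Protocol Section 6.1.3 (Sample size) takes as clinically relevant "at least 2% absolute difference in Flow mediated dilatation (FMD) (corresponding to 20-30% relative difference". It then sets the hypotheses. The null is "With the null hypothesis being that CFZ/Dex therapy is associated with <10% relative difference in FMD". The alternative is at or above 30%: "30% difference is considered as significant, and with an a=0.05". From these, "a sample of 40 patients is required for 90% power of detecting these differences (all tests are 2-sided". Enrolment is raised to 46 for 15% dropout. The source is given only as "Sample size calculation is made on the basis of previous data"; no SD, within-patient correlation, visit or test is named.

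Protocol Section 8 (Data presentation and statistical analysis) states the test: "Repeated measures ANOVA will be performed in order to assess significant variations of parameters of interest over time". Linear mixed models are added to adjust for confounders. The significance rule is general: "All tests will be two-tailed and statistical significance will be considered for P" values under 0.05. Section 8 mentions neither a 10% bound nor a particular FMD contrast.

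The Study Synopsis (Endpoints) defines the primary endpoint as "Changes in hemodynamic markers (peripheral and aortic office blood pressure and 24 hour ambulatory BP monitoring parameters", together with endothelial function, arterial stiffness and wave reflections. FMD enters as the measure of endothelial function and is not ranked above the rest.

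**The concern.** The protocol fixes both a hypothesis and a test, and they do not match. The sized null is an interval: any change smaller than 10% counts as no relevant effect. The null of a repeated measures ANOVA is a single point, equal means at all times. A significant result shows that FMD moved. It does not show that it moved by more than 10%, let alone by the 20-30% that Section 6.1.3 calls relevant.

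At stake is how the main result will be read. A reader who takes the sample size section at its word would treat P below 0.05 as evidence against a change under 10%. The planned analysis cannot supply that evidence, and the quoted 90% does not describe it. For blood pressure, stiffness and wave reflections, the protocol gives no power basis at all.

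**Working it through.** **Inputs from Section 6.1.3:** null bound 10%, alternative 30%, two-sided alpha 0.05 (z = 1.960), power 90% (z = 1.2816), n = 40. **Not given:** any SD. SDs below are assumptions, in percentage points of within-patient relative FMD change.

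**1. Can 40 be reproduced?**

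- As a mean change: no, because n = [(1.960 + 1.2816) × SD / 20]² needs an SD.
- With 10% and 30% read as proportions of patients in a one-sample test:
  - normal approximation: (1.960√0.09 + 1.2816√0.21)² / 0.20² = 34.5, so 35;
  - with continuity correction: (34.53/4) × [1 + √(1 + 2/(34.53 × 0.20))]² = 39.4, so 40;
  - arcsine: (1.960 + 1.2816)² / (2asin√0.30 − 2asin√0.10)² = 10.51 / 0.516² = 39.5, so 40.

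The figure therefore matches a proportion calculation, but that this is where it came from is an inference.

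**2. The SD that 40 would imply for a mean change.** Shift = 30 − 10 = 20 points. Normal approximation: SD = 20 × √40 / 3.2416 = 39.0. Noncentral t with 39 degrees of freedom: SD = 38.0.

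**3. The zero null, approximated by one before/after paired t-test.** Noncentrality = (true change / SD) × √40. At SD 38:

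- true 5%: 0.83, significant in 12.8% of trials;
- true 10%: 1.66, significant in 36.8%;
- true 20%: 3.32, significant in 90.0%;
- true 30%: 4.99, significant in 99.8%.

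Across assumed SDs, n = 40, tested against zero:

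| SD | true 5% | true 10% | true 30% |
|---|---|---|---|
| 30 | 17.7% | 53.8% | >99.9% |
| 38 | 12.8% | 36.8% | 99.8% |
| 50 | 9.5% | 23.5% | 95.9% |
| 60 | 8.1% | 17.7% | 86.9% |

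**4. The omnibus ANOVA itself.** The Section 7 schedule has 13 vascular study columns. Six carry the mark for two measurements, giving 13 + 6 = 19 occasions. Assume compound symmetry and a per-occasion SD of 38/√2 = 26.9. A true 10% shift is then significant in 21% of trials if one occasion moves and 85% if six do; a true 5% shift in 8% and 23%. The single-contrast result is not an artefact of the simplification.

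**5. Coverage.** Peripheral office BP, aortic office BP, ambulatory BP parameters, FMD, stiffness and wave reflections make at least six primary measures. The sizing inputs concern FMD only, so no power can be computed for the other five.

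**The case against.** This is a single-arm observational study with a partly descriptive aim. An unseen statistical analysis plan may name the contrast, and the cited earlier data may contain an SD. This stands in part: the lack of detail in Section 8 is not itself a fault, and all that can be said about 40 is that the text does not allow it to be verified. But added detail would not remove the conflict, because the protocol has already stated both a null and a test.

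The error figures depend on an assumed SD, and 10% is the boundary of the stated null, hence its worst case. That is right. Well inside the null, at 5%, the rate is about 13%: above 5%, but moderate.

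Three stronger readings are tempting, and the documents support none of them.

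- **A reader might infer that the study is underpowered for FMD.** Power for 30% against the 10% bound does fall to 69% at SD 50 and 54% at SD 60, but that test is not planned. Against zero, the corresponding figures are 96% and 87%. Moving the null from 10% to zero raises power.
- **A reader might infer a family-wise error of 26%** (1 − 0.95⁶ for six independent tests; about 21% at correlation 0.5). This needs a rule that one significant measure makes the study positive. The protocol states no such rule, and multiplicity may be handled in the analysis plan.
- **A reader might infer that FMD changes were mistaken for response rates.** The numerical match is close, but two formulas give 40 and the actual calculation is not shown.

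**Conclusion.** The mismatch is real and rests on the text alone: Section 6.1.3 sizes an interval null for FMD, and Section 8 tests a null of no change. Three consequences follow without assumptions. The 90% is not the power of the planned test, it says nothing about the other primary measures, and 40 cannot be checked as a sample size for a mean change.

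The size of the effect on interpretation does need an assumed SD. At 38 points, a test against zero is significant in about 13% of trials at a true 5% change and 37% at 10%; the latter figure is 54% at SD 30 and 24% at SD 50. P below 0.05 therefore cannot stand for the effect that the protocol calls clinically relevant. This is a mismatch in what a significant result means; it does not show that 40 patients are too few for FMD.

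**What to change.** In Sections 6.1.3 and 8, name one FMD contrast, baseline to one named visit, as the sized analysis. Report its mean within-patient relative change with a two-sided 95% CI. Then choose one of two routes.

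- **(a) Keep the 10% bound.** Claim a change beyond the stated null only if the whole CI lies beyond 10%. Restate the size as: 40 completers give 90% power for 30% against 10% if the SD of within-patient relative change is at most about 38 points.
- **(b) Restate the null as no change.** Give the power of 40 completers under a stated SD. At SD 38 this is 99.8% for a 30% change and 90% for 20%; at SD 60 it is 87% for 30%. Relevance is then judged from the CI, not from the P value.

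Under either route, say that the power statement applies to FMD only. The other measures can stay in the primary endpoint, reported with CIs.

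The cost is wording, with no extra patients. The stated power becomes conditional on an assumed SD. Route (a) is also demanding at the low end of the relevant range: a true 20% change lies only 10 points beyond the bound, so at SD 38 its power is the same 37% or so found above for a 10-point shift.
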